#### 4.3.3 Prohibited Medications

The following medications are prohibited during the study (unless utilized to treat a drug related adverse event):

- Immunosuppressive agents
- Immunosuppressive doses of systemic corticosteroids (except as stated in Section 5.5.2 above)
- Any concurrent anti-neoplastic therapy (ie, chemotherapy, hormonal therapy, immunotherapy, extensive, non-palliative radiation therapy, or standard or investigational agents or devices for treatment of glioblastoma)
- Antiviral treatment for HBV or HCV
- Caution should be applied in the administration of over-the-counter medications and herbal preparations during the conduct of the study. Consultation with the Sponsor is encouraged.

If there is a clinical indication for one of these or other medications or vaccinations specifically prohibited during the trial, discontinuation from trial therapy or vaccination may be required. The treating investigator should discuss any questions regarding this with the overall study PI or his designee. The final decision on any supportive therapy or vaccination rests with the treating investigator.

#### 4.3.4 Other Restrictions and Precautions

It is the local imaging facility's responsibility to determine, based on subject attributes (e.g., allergy history, diabetic history and renal status), the appropriate imaging modality and contrast regimen for each subject. Imaging contraindications and contrast risks should be considered in this assessment. Subjects with renal insufficiency should be assessed as to whether or not they should receive contrast and if so, what type and dose of contrast is appropriate.

Specific to MRI, subjects with severe renal insufficiency (ie, estimated glomerular filtration rate [eGFR] < 30 mL/min/1.73m^2) are at increased risk of nephrogenic systemic fibrosis. MRI contrast should not be given to this subject population. In addition, subjects are excluded from MRI if they have metallic implants, MRI-incompatible pacemakers, etc. The ultimate decision to perform MRI in an individual

CONFIDENTIAL

This material is the property of the NYU School of Medicine. Do not disclose or use except as authorized in writing by the study sponsor

subject in this study rests with the site radiologist, the investigator, and the standard set by the local Ethics Committee.

#### **4.4 Subject Recruitment and Screening**

All efforts will be made to actively recruit and retain women and members of minority groups and their subpopulations in this study, with the objective of accruing a study population that resembles the age, gender, ethnic and racial composition of the adult U.S. population as closely as possible. The inclusion and exclusion criteria in this study should not have a negative effect on the enrollment of these populations. If any differences are observed in the outcomes of these populations, these results will be reported.

Target enrollment for this study is 24 patients over 18 months. The target accrual goal is 16 patients per year. Patients will be recruited for the study from investigator or sub-investigator clinical practices. Identification of prospective subjects will be conducted by reviewing the medical records of patients in the investigator or sub-investigator's clinical practice and the investigator and sub-investigators will use all efforts to limit its use of protected health information. For study requirements to maintain subject confidentiality and management of study information according to the requirements of the Health Insurance Portability and Accountability Act of 1996 (HIPAA), refer to Section 9.

Informed consent will take place in the investigator or sub-investigator's clinical practice per institutional guidelines when a patient is deemed potentially eligible for participation by the study investigator or sub-investigator. Patients will be asked to give medical information about themselves specific to the inclusion and exclusion criteria outlined in the protocol. Only study investigators will have access to this information. Information collected will include Participant Demographics (address, zip code, sex, race, ethnicity, initials, date of birth), Parameters for eligibility, Parameters for exclusion, and Parameters for stratifications.

The Investigator or Sub-Investigator will:

1. Obtain signed and dated informed consent from the potential subject before any study specific procedures are performed.
2. Determine patient eligibility (See Section 4)
3. Submit registration/eligibility packet to the Research Coordinator at NYUSoM Perlmutter Cancer Center CTO.
4. Receive registration confirmation from the Research Coordinator at NYUSoM Perlmutter Cancer Center CTO, including a unique study identification number assigned to the patient by the research coordinator, which will be distributed to the study team upon registration of the patient.

The informed consent process and documentation follows the established procedures of the NYUSoM Perlmutter Cancer Center Clinical Trials Office.

##### **4.4.1 Informed Consent**

Consent will be obtained only by a participating investigator who has completed requisite training for human subject research and has been instructed by the Principal Investigator about the research study and consent process. The participating investigator must assess the subject's capacity to provide informed consent to ensure subjects who lack capacity to provide informed consent are not enrolled. The assessment should include open-ended questions (i.e., not yes or no questions) regarding the purpose and involvement of the research. The investigator evaluating patient capacity must be an M.D. with experience in evaluating patient capacity. Investigators will review the informed consent form with patients and address any questions or concerns prior to obtaining written informed consent for participation and HIPAA authorization.

CONFIDENTIAL

This material is the property of the NYU School of Medicine. Do not disclose or use except as authorized in writing by the study sponsor

Patients who are evaluated and/or treated by physicians in the oncology program will be given a consent form describing participation in the study. Patients will be given adequate time to read the consent form. They will be given time to ask questions about the study in private exam rooms. Questions will be answered by a participating physician, nurse practitioner, or research nurse all of whom have completed requisite training for human subject research. Investigators will review the informed consent form with patients and address any questions or concerns prior to obtaining written informed consent for participation. Investigators will stress that participation in the study is completely voluntary and will not affect the care patients receive or result in any loss of benefits to which patients are otherwise entitled.

For non-English speaking patients, institutional translation services will be utilized. All procedures for consenting non-English speaking patients will be in accordance with NYU Langone Health PCC CTO guidelines and policies.

For patients who cannot read, a witness, not related to the research study will be present. The consent will be read to the patient. The patient will also be allowed to ask any questions s/he may have. The investigator will ask the patient questions to ensure s/he understands the study. If the investigator determines the subject understands the study, the patient will mark an X where his/her name would go and the witness will sign the consent form.

#### **4.4.2 Documentation of Consent**

The Principal Investigator or IRB-approved sub-investigator will be responsible for documentation in the medical record that consent has been obtained from all participants. A signed copy of the consent form will be given to each participant. Original consent forms and informed consent checklists will be stored in the subject's medical chart/study binder. If there are any amendments made to the protocol after initial IRB approval, all subjects will have re-consents that will also be stored in the subject's medical chart/study binder.

### **4.5 Registration Procedures**

#### **4.5.1 General Guidelines**

Each patient must sign and date an informed consent form before undergoing any study specific procedure unless a procedure is being performed as part of the patient's standard of care.

Enrollment in the study requires that all inclusion and exclusion criteria have been met. Enrollment occurs upon confirmation of registration from the NYU School of Medicine PCC Clinical Trials Office (CTO). The following materials must be submitted to the Research Coordinator for registration:

1. Complete signed and dated informed consent form
2. Complete signed and dated informed consent checklist
3. Complete signed and dated eligibility checklist
4. All supporting documentation verifying each criterion has been met

Registration will occur within 48 hours of research coordinators' receipt of all the above documents. A written confirmation of enrollment including a unique study identification number assigned by the research coordinator will be distributed to the study team upon registration.

Pretreatment evaluation will therefore be dictated by standard clinical practice. Eligible patients will be entered into the study by the study coordinator.

All patients will be required to sign a written informed consent prior to being registered on this study. Any patient not registered to the study before treatment begins will be considered ineligible and registration will be denied. Every effort will be made to answer questions raised by patients and their families or

CONFIDENTIAL

This material is the property of the NYU School of Medicine. Do not disclose or use except as authorized in writing by the study sponsor

advocates regarding the protocol and alternative therapies prior to asking a patient to sign the consent form.

Once eligibility is verified, a unique patient study number will be issued within 24 hours of receiving all required registration material. The patient will not be identified by name. This is the point, at which, the patient is considered on the study. Subjects must not start any protocol study specific procedures, unless part of standard of care prior to registration

Issues that would cause treatment delays should be discussed with the Overall Principal Investigator.

## 5 Study Drugs and Treatment Regimen

### 5.1 Description and Packaging

The study drugs must be stored in accordance with the environmental conditions (temperature, light, and humidity) as determined by the IB and/or package insert. If concerns regarding the quality or appearance of the study drug arise, the study drug should not be dispensed and contact the Sponsor immediately.

#### 5.1.1 Nivolumab (BMS company code: BMS-936558)

Nivolumab (Opdivo®; Bristol-Myers Squibb) is a human IgG4 mAb that blocks the interaction between PD-1 and its ligands, PD-L1 and PD-L2. Binding of the PD-1 ligands, PD-L1 and PD-L2, to the PD-1 receptor found on T cells, inhibits T-cell proliferation and cytokine production. Upregulation of PD-1 ligands occurs in some tumors and signaling through this pathway can contribute to inhibition of active T-cell immune surveillance of tumors. Nivolumab is US FDA-approved as a monotherapy in BRAF wild type advanced melanoma after failing ipilimumab and in BRAF V600 mutation-positive advanced melanoma after failing a BRAF inhibitor. Nivolumab in combination with ipilimumab is US FDA-approved in BRAF wild type advanced melanoma with or without prior therapies. Further details regarding the clinical experience with nivolumab may be found in the current version of the FDA-approved Opdivo® label.

Nivolumab product is a clear to opalescent colorless to pale yellow liquid that may contain particles.

Nivolumab is presented at a concentration of 10 mg/mL in single-use glass vials containing 100 mg of nivolumab. Each vial is 10 mL per volume.

Nivolumab will be packaged in a labeled carton box with 5-10 labeled vials (open-label). Each single-use 10 mL vial contains 100 mg of nivolumab (10 mg/mL).

Nivolumab drug product must be stored at 2°C to 8°C until use, and it must not be frozen. Nivolumab drug product must be protected from light.

#### 5.1.2 Ipilimumab (BMS company code: BMS-734016, MDX-010)

Ipilimumab (Yervoy®; Bristol-Myers Squibb) is a fully human mAb (IgG1κ) that binds to the CTLA-4, a negative regulator of T-cell activity. Ipilimumab binds to CTLA-4 and blocks the interaction of CTLA-4 with its ligands, CD80/CD86. Blockade of CTLA-4 has been shown to augment T-cell activation and proliferation, including the activation and proliferation of tumor infiltrating T-effector cells. Inhibition of CTLA-4 signaling can also reduce T-regulatory cell function, which may contribute to a general increase in T-cell responsiveness, including the anti-tumor immune response. Combined nivolumab- (anti-PD-1) and ipilimumab-mediated inhibition results in enhanced T-cell function that is greater than the effects of either antibody alone, and results in improved anti-tumor responses in metastatic melanoma. Ipilimumab is US FDA-approved in the treatment of advanced melanoma as a monotherapy (irrespective of BRAF V600 mutation status) and in combination with nivolumab in patients with BRAF wild type disease.

CONFIDENTIAL

This material is the property of the NYU School of Medicine. Do not disclose or use except as authorized in writing by the study sponsor

Further details regarding the clinical experience with ipilimumab as SA and in combination with nivolumab may be found in the current version of the approved Yervoy® and Opdivo® labels, respectively.

Ipilimumab injection, 200 mg/40 mL (5 mg/mL), is formulated as a clear to slightly opalescent, colorless to pale yellow, sterile, nonpyrogenic, single-use, isotonic aqueous solution that may contain particles.

Ipilimumab injection, 200 mg/40 mL, is supplied in 10-cc or 50-cc Type I flint glass vials, respectively, stoppered with gray butyl stoppers and sealed with aluminum seals. The drug product is formulated at a concentration of 5 mg/mL at a pH of 7.0.

Ipilimumab will be packaged in a labeled carton box with 4 labeled vials (open-label). Each single-use 40 mL vial contains 200 mg of ipilimumab (5 mg/mL).

Ipilimumab drug product must be stored at 2°C to 8°C until use, and it must not be frozen. Ipilimumab drug product must be protected from light.

## **5.2 Treatment Regimen**

### **5.2.1 Nivolumab and Ipilimumab**

After screening procedures and registration, all subjects will be treated with study treatment, which should begin as close as possible to the date on which the participant is registered.

Nivolumab and ipilimumab will be administered in an outpatient setting as intravenous (IV) infusions; however, inpatient administration is permitted. Nivolumab and ipilimumab will be provided to patients enrolled on this study by BMS.

Nivolumab 3 mg/kg IV will be given as a 30-minute infusion every 2 weeks ( $\pm 3$  days of the scheduled day of drug administration).

Ipilimumab 1 mg/kg IV will be given as a 30-minute infusion every 6 weeks ( $\pm 5$  days of the scheduled day of drug administration).

Nivolumab and ipilimumab administration will start on Day 1 and both study drugs will continue for 2 years (defined as 96 weeks, corresponding to 16 anticipated cycles) or until disease progression, unacceptable toxicity, withdrawal of consent, the study ends, or until another protocol withdrawal criterion is met, whichever occurs first.

One treatment cycle is defined as 42 days (6 weeks), corresponding to 2 doses of nivolumab and one dose of ipilimumab.

There will be no dose escalations or reductions allowed.

Doses of nivolumab and/or ipilimumab may be interrupted, delayed, or discontinued depending on how well the subject tolerates the treatment. See section 6.2 for additional information.

### **5.2.2 Radiation Therapy**

RT must be provided at the study site (NYUSoM).

On Day 8 of Cycle 1 (7 days after initiation of study drugs), all subjects will begin HFRT to a total dose of 45 Gy, given in 15 fractions of 3 Gy.

CONFIDENTIAL

This material is the property of the NYU School of Medicine. Do not disclose or use except as authorized in writing by the study sponsor

### 5.2.2.1 Technique

Intensity modulated radiotherapy (IMRT) via any method (e.g., VMAT, static field IMRT) or Stereotactic Radiotherapy (SRT) is required. Any FDA cleared external beam radiation delivery system may be used (including conventional linear accelerators, cyberknife systems, tomotherapy, proton therapy, etc.). Treatment at NYUSoM will be on Varian LINAC (TrueBeam or Edge). or Elekta Gamma Knife Icon Unit.

### 5.2.2.2 Dose Specifications

**Photons:** Treatment shall consist of 45 Gy delivered in 15 fractions. The treatments may extend over the weekend (e.g., 15 treatments delivered over 3-4 weeks). Target coverage and homogeneity limits and deviations are listed in **Table A1**.

**Table A1: Target Coverage and Dose Limits**

Dose Metric	Per Protocol	Variation Acceptable	Deviation Unacceptable
Volume of PTV covered by the prescription dose of 45 Gy photons	Greater than or equal to 95% of the PTV should receive greater than or equal to 45 Gy photons	Greater than or equal to 90% of the PTV receiving greater than or equal to 45 Gy photons	Less than 90% of the PTV receiving greater than or equal to 45 Gy photons. Coverage less than 90% is acceptable in areas of OAR/PTV overlap.
Minimum dose to the PTV (0.03 cc)	Greater than or equal to 40.5 Gy (90% of the prescription dose) photons	Greater than or equal to 38.25 Gy (85% of the prescription dose) photons	Less than 38.25 Gy (85% of the prescription dose) photons
Maximum dose to the PTV (0.03 cc)	Less than or equal to 48.6 Gy (108% Rx Dose) photons. For SRT, this represents a plan prescribed to the 84% or greater Isodose line)	Less than or equal to 49.5 Gy (110% Rx Dose) photons. For SRT, this represents a plan prescribed to the 80% isodose line)	Greater than 49.5 Gy (110% Rx Dose) photons. or an isodose line less than 80% for a radiosurgical plan)

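### In Table A1, the isodose lines given for stereotactic plans do not match the maximum doses they are said to represent

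*Combined protocol and SAP*

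**What the plan says.** Section 5.2.2.2 fixes the prescription: "Treatment shall consist of 45 Gy delivered in 15 fractions". It introduces Table A1 as a table of target coverage and homogeneity limits. The row for maximum dose to the PTV, taken over 0.03 cc, has three columns:

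- **Per Protocol:** "Less than or equal to 48.6 Gy (108% Rx Dose) photons", followed by the statement that, for SRT, "this represents a plan prescribed to the 84% or greater Isodose line".
- **Variation Acceptable:** "Less than or equal to 49.5 Gy (110% Rx Dose) photons", followed by "For SRT, this represents a plan prescribed to the 80% isodose line".
- **Deviation Unacceptable:** "Greater than 49.5 Gy (110% Rx Dose) photons. or an isodose line less than 80% for a radiosurgical plan".

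The SRT wording can come into play. Sections 5.2.2.1 and 5.2.2.3 require either IMRT or SRT, and the equipment listed for the study site includes a Gamma Knife ("or Elekta Gamma Knife Icon Unit" in Section 5.2.2.1). The protocol does not define the dose that counts as 100% for an isodose line, and it does not exempt SRT plans from the Gy limits.

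**The concern.** The first two cells each give one limit in two units, Gy with percent of prescription and, for SRT, an isodose line, and state that the second represents the first. If the two are not equivalent, an SRT plan can be classified differently depending on which half of the cell the reader applies. The third cell sharpens this, because it joins its two conditions with an or: exceeding 49.5 Gy is enough by itself to make a plan unacceptable.

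What is at stake is whether a stereotactic plan is accepted and how a departure is recorded. Section 5.2.2.7 asks for isodose distributions to be submitted at completion of treatment. Someone checking them against Table A1 could not classify a range of SRT plans consistently.

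**Working it through.** **Inputs.** Prescription 45 Gy (Section 5.2.2.2). Caps of 48.6 Gy (108%) and 49.5 Gy (110%), and isodose lines of 84% and 80% (Table A1, maximum-dose row).

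**Step 1: the table's own percentages.** Dose = 45 × percent of prescription.

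- 45 × 1.08 = 48.6 Gy
- 45 × 1.10 = 49.5 Gy

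The Gy and percent figures agree with each other.

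**Step 2: the isodose lines.** Taking 100% as the plan maximum, maximum dose = prescription ÷ isodose fraction.

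- 84% line: 45 ÷ 0.84 = 53.57 Gy, and 53.57 ÷ 45 = 119.0%. Stated: 48.6 Gy. Gap: 53.57 − 48.6 = 4.97 Gy.
- 80% line: 45 ÷ 0.80 = 56.25 Gy, and 56.25 ÷ 45 = 125.0%. Stated: 49.5 Gy. Gap: 56.25 − 49.5 = 6.75 Gy.

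In percent of prescription the gaps are 119 − 108 = 11 and 125 − 110 = 15 points.

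**Step 3: the lines that would match the caps.**

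- 45 ÷ 48.6 = 92.6%
- 45 ÷ 49.5 = 90.9%

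**Step 4: does another reference dose rescue the pairs?** If each pair were a true equivalence, cap × isodose fraction would return 45 Gy. It gives 48.6 × 0.84 = 40.8 Gy and 49.5 × 0.80 = 39.6 Gy. Put the other way, 45 Gy at the 84% line places the 100% reference at 53.57 Gy, and at the 80% line at 56.25 Gy. Both exceed the caps on the PTV maximum in their own cells. For the pairs to hold, the reference point would have to lie outside the PTV or in a hot spot smaller than 0.03 cc, and the protocol says neither.

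**Step 5: classification of an SRT plan, read literally.** The 80% cell is taken to cover 80% up to just under 84%, since the unacceptable column starts below 80%.

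| SRT plan prescribed to | By isodose wording | By Gy limit |
|---|---|---|
| 92.6% or above | Per Protocol | Per Protocol |
| 90.9% to just under 92.6% | Per Protocol | Variation Acceptable |
| 84% to just under 90.9% | Per Protocol | Deviation Unacceptable |
| 80% to just under 84% | Variation Acceptable | Deviation Unacceptable |
| Below 80% | Deviation Unacceptable | Deviation Unacceptable |

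The two scales agree only at 92.6% and above, or below 80%.

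**The case against.** The strongest reply is that the row sets two separate tracks: Gy limits for IMRT and isodose limits for SRT. Each isodose clause is addressed to SRT or to a radiosurgical plan. If the 49.5 Gy ceiling already bound SRT, the clause about lines below 80% would add nothing, because any such plan exceeds 56.25 Gy. On this reading every plan has one class and the fault is loose phrasing.

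The reading is possible, and it means the double classification follows from the literal wording and not from every reading. It does not clear the text. The first two cells assert an equivalence and do not set a separate criterion for SRT. The redundancy is also what one would expect from an author who believed 80% and 110% were the same limit. If two tracks were meant, the table has to say so.

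Three further objections stand:

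- **Not stated to be a safety limit.** A reader might infer that a safety limit for normal tissue is compromised. The documents do not support that. Table A1 is introduced as covering coverage and homogeneity. The limits for the optic structures and brainstem are in Table A2, the pituitary has its own constraint in Section 5.2.2.2, and none of these uses the disputed cells.
- **The link to dose-limiting toxicity is not stated.** A reader might infer that a subject's DLT evaluability turns on this row, since Sections 6.1.1 and 7.3.1 require radiotherapy to have been completed as the protocol specifies. Neither section refers to Table A1, and under Section 7.3.1 a subject who has a DLT is evaluable in any case. An effect is possible but not stated.
- **The gaps are approximate.** The row limits dose to 0.03 cc of PTV, whereas an isodose percentage is usually tied to a point maximum. For a maximum inside the PTV, 4.97 and 6.75 Gy are therefore upper estimates. Nothing in the documents suggests that this difference in metric accounts for gaps of that size.

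**Conclusion.** The isodose equivalents in the maximum-dose row are wrong as written: they do not represent the Gy limits beside them. The mismatch is about 5.0 Gy (11 points of prescription) in the per-protocol column and 6.75 Gy (15 points) in the acceptable-variation column. These sizes assume that isodose percentages are relative to a plan maximum equal to the 0.03 cc PTV maximum.

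Only SRT plans are exposed, and among them those prescribed from 80% to just under 92.6%. The documents do not say how many subjects will be treated with SRT. Sample size, power and the efficacy analyses do not depend on this row. The analysis populations in Sections 7.3.2 to 7.3.4 are defined by receipt of study drug, with re-resection added for the surgical cohort, and not by radiotherapy plan class. The arithmetic shows that the two scales conflict; it does not show which one was intended.

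**What to change.** The radiotherapy team should revise this one row so that each plan has a single classification:

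1. Reconcile the Gy and percent limits with the isodose wording in all three columns.
2. Define the reference dose to which an isodose percentage refers.
3. State whether the Gy ceiling applies to SRT plans or whether SRT is judged by isodose alone.

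If completing radiotherapy as specified, in Sections 6.1.1 and 7.3.1, is meant to depend on the Table A1 categories, those sections should say so. Which limit is right is for the radiotherapy team to decide; this review proposes none. The cost is a correction to one table row, with no change to the design or analysis.
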